### **4.4 Adherence**

The Investigator may make no changes or amendments to this protocol after the protocol has been agreed to and signed by all parties unless such change(s) or amendment(s) have been thoroughly discussed and agreed upon by the Investigator, the IRB, or the sponsor. Any change or amendment decided upon will be recorded in writing, the Investigator and the Sponsor will sign the written agreement, and the signed agreement will be appended to this protocol.

## **5 STUDY INTERVENTIONS**

### **5.1 Interventions, Administration, and Duration**

No intervention or administration will be performed due to the observational nature of each phase. Charts of patients enrolled in the study will be reviewed for an initial monitoring method, any changes in

management, including AAD, OAC, CA, as per physicians' preference, arrhythmia recurrence, need for redo CA, and AF-related complication, for 12 months after enrollment. Lastly, the primary outcomes of AF freedom and continued AAD and OAC use will be noted at the end of the study duration.

## 5.2 Handling of Study Interventions

Screening, enrollment, and data collection will be performed by the Electrophysiology team and Kansas City Heart Rhythm Research Foundation (KCHRRF) members or respective institutions. Once data is collected, it will be analyzed by KCHRRF staff.

## 6 STUDY PROCEDURES

### 6.1 Description of Evaluation

*Table 1. Variables for data collection will include but are not limited to the following.*

Variables	Description and Definition
Age	## Years
Gender	0 = Male, 1 = Female
BMI	## kg/m2
Race	0 = Caucasian, 1 = African American, 2 = Hispanic, 3 = Asian, 4 = Other
Hypertension	0 = No, 1 = Yes
Hyperlipidemia	0 = No, 1 = Yes
Diabetes Mellitus	0 = No, 1 = Yes
Coronary Artery Disease	0 = No, 1 = Yes
CVA/TIA	0 = No, 1 = Yes
Peripheral Artery Disease	0 = No, 1 = Yes
Obstructive Sleep Apnea	0 = No, 1 = Yes
Compensated HF (EF > 35%)	0 = No, 1 = Yes
History of Smoking	0 = No, 1 = Yes
Thyroid Dysfunction	0 = None, 1 = Hypothyroidism, 2 = Hyperthyroidism
Chronic Obstructive Pulmonary Disease	0 = No, 1 = Yes
Gastrointestinal Disorders	0 = No, 1 = Yes
CHADS 2 /VASC 2 Score	##
Antiarrhythmic Drug	
History of Cardioversion	0 = No, 1 = Yes
Baseline AAD Use	0 = No, 1 = Yes
Duration of Arrhythmia	## Mos.
Left Atrial Size	## cm.
Left Ventricular Ejection Fraction	## %
Access to EP	0 = No, 1 = Yes
Compliance to OAC	0 = No, 1 = Yes
Attempted AAD	0 = No, 1 = Yes
Need for Catheter Ablation	0 = No, 1 = Yes
Time to Catheter Ablation	## Days
Number of Monitors used Post-CA	##

Type of Monitors Used	0 = MCOT, 1 = 48-Hr Holter
Need for Redo Ablation	0 = No, 1 = Yes
Time to Redo Ablation	## Days
CV-Related Hospital Duration	## Days
Length of Stay	## Days
AF-Related Hospitalization	0 = No, 1 = Yes
HF-Related Hospitalization	0 = No, 1 = Yes
Bleeding Complication	0 = No, 1 = Yes
Stroke and TIA	0 = No, 1 = Yes
Freedom of AF at 12 Mos.	0 = No, 1 = Yes
Continued OAC Use	0 = No, 1 = Yes
Continued AAD Use	0 = No, 1 = Yes

Abbreviations: BMI – body mass index, CVA = cerebrovascular accident, TIA – transient ischemic attack, AAD = antiarrhythmic drug, CV – cardiovascular, CA = catheter ablation, AF – atrial fibrillation, HF – heart failure, OAC – oral anticoagulation, MCOT – mobile cardiac outpatient telemetry

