## **2 BACKGROUND AND RATIONALE**

### **2.1 Background on Condition, Disease, or Other Primary Study Focus**

AF is the most frequent cardiac arrhythmia, with a global prevalence that is only expected to increase. A significant number of patients – up to 38% – may be asymptomatic, making management more difficult. [1] Regardless of symptoms, AF is associated with significant morbidities, including but not limited to heart failure, stroke, dementia, and death.

The management of AF is complex, with clinical decisions related to rate and rhythm control strategies with AADs and CA and stroke prevention. Like other chronic diseases, frequent routine assessments help select, assess, and change management strategies. Implantable cardiac monitors (ICMs) are another option that store electrocardiogram (ECG) tracings for years at a time, enabling continuous monitoring, assessment of AF burden, and therapy efficacy. Previous studies have demonstrated a threefold increase in AF detection, including asymptomatic AF in cryptogenic stroke, syncope, and after CA. using ICMs.[2-4] Their use in AF management has gained popularity for this reason.

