### **2.2 Study Rationale**

Even with its increasing popularity and use, the impact of ICMs on AF management is still being determined and can even be conflicting. Furthermore, the use of ICM is dependent on physician preference. We hypothesize that dynamic monitoring with ICMs is superior to conventional methods and should be used for all patients with AF. Thus, we aim to measure the outcomes of using ICM versus more traditional approaches in patients with AF.

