### **4.2 Inclusion Criteria**

- Patients > 18 years of age
- Present for management of AF
- ICM is inserted at the discretion of the treating physician

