## 6.2 Randomization

No randomization will occur due to the nature of the study.

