## 9.4 Data Analyses

Statistical analysis will be performed on both continuous and categorical variables. As appropriate, continuous variables will be reported as mean  $\pm$  standard deviation and compared with two-tailed T-tests and Mann-Whitney testing. Categorical variables will be reported as frequency and percentages and compared with Chi-square testing as appropriate. Cox proportional regression models will be used for hazard ratios and confidence intervals. A p-value  $< 0.05$  will be used to determine statistical significance. Kaplan-Meier graphs will be calculated when appropriate. We will use SPSS [IBM, Armonk, New York] for all statistical analysis.

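### AF symptom status at entry is not a listed variable, so the plan does not assure that a plausible confounder of CA and AAD decisions can be checked or adjusted for

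*Combined protocol and SAP*

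**What the plan says.** Section 6.1 introduces Table 1 with the words "Variables for data collection will include but are not limited to the following". The rows cover demographics, comorbidities (including gastrointestinal disorders and thyroid dysfunction), stroke risk score, cardioversion history, baseline AAD use, arrhythmia duration, left atrial size and ejection fraction, followed by treatments and outcomes. None records symptoms, and no other section plans to.

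Section 2.1 puts the asymptomatic share at up to 38% and says such patients "may be asymptomatic, making management more difficult".

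On how patients come to have an ICM, section 4.2 says "ICM is inserted at the discretion of the treating physician", section 2.2 says "the use of ICM is dependent on physician preference", and section 6.2 says "No randomization will occur due to the nature of the study". On treatment, section 5.1 has charts reviewed for changes in "management, including AAD, OAC, CA, as per physicians' preference, arrhythmia recurrence, need for redo CA".

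Section 9.3 lists time of AAD initiation, time to CA, arrhythmia recurrence and redo ablation among the primary outcomes, and AF and cardiovascular hospitalization among the secondary ones. For analysis, section 9.4 says "Cox proportional regression models will be used for hazard ratios and confidence intervals". It names no covariates, matching or weighting.

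**The concern.** Several primary outcomes are treatment decisions. Whether and when a patient is offered an AAD or an ablation plausibly depends on how symptomatic that patient is. Choice of monitor is also a physician's decision and may depend on the same thing. If the arms differ in the share of asymptomatic patients, time to CA, AAD initiation and redo ablation can differ between them even if monitoring has no effect, and the difference would be read as an effect of the ICM.

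If abstraction follows Table 1 as listed, the baseline table cannot show whether the arms are alike in symptoms, and no model can include the item. A larger sample does not help: the bias stays the same while the standard error shrinks, so a false difference becomes more likely to reach significance.

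**Working it through.** **Plan figures.** No figure in the plan bears directly on this point. The 99% power in section 9.2 comes with no event rates or effect size and cannot be reproduced. Only the 1250 per arm is taken from that section.

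**Inputs from the documents**
- 1250 patients per arm (sections 4.1.2 and 9.2).
- Asymptomatic share of up to 38% (section 2.1).
- Significance at p < 0.05 (section 9.4), taken as two-sided.

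**Assumptions, not in the documents**
- 12-month CA rates in symptomatic (pS) and asymptomatic (pA) patients.
- The asymptomatic share a in each arm.
- No true ICM effect, and fixed arms.

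**Formulas**
- Arm CA rate = (1 − a) × pS + a × pA.
- Gap between arms = (difference in a) × (pS − pA).
- Expected z = gap / √[2 × p̄ × (1 − p̄) / 1250], where p̄ is the mean of the two arm rates.
- The chance of p < 0.05 comes from the two-sided pooled two-proportion z test.

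**Worked case: pS = 40%, pA = 15%; asymptomatic 38% (ICM) v 19% (non-ICM)**
- ICM arm: 0.62 × 40% + 0.38 × 15% = 24.8% + 5.7% = 30.5%.
- Non-ICM arm: 0.81 × 40% + 0.19 × 15% = 32.4% + 2.85% = 35.25%.
- Gap: 4.75 points. With p̄ = 0.32875, the standard error is √(2 × 0.32875 × 0.67125 / 1250) = 0.0188, so z = 0.0475 / 0.0188 = 2.53.
- Chance of a false significant result: about 72%.

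**Other cases with 38% asymptomatic in the ICM arm**

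| Non-ICM asymptomatic share | pS / pA | Gap (points) | Chance of p < 0.05 |
|---|---|---|---|
| 33% | 40% / 15% | 1.25 | 10% |
| 28% | 40% / 25% | 1.5 | 12% |
| 28% | 40% / 15% | 2.5 | 27% |
| 19% | 40% / 25% | 2.85 | 32% |
| 10% | 40% / 15% | 7.0 | 96% |

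**Second grid: mean asymptomatic share 38%, split evenly about that value.** The three pS / pA pairs are 40/30, 50/30 and 50/20.

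| Imbalance between arms | Gap (points) | Chance of p < 0.05 |
|---|---|---|
| 5 points | 0.5, 1.0, 1.5 | 6%, 8%, 12% |
| 10 points | 1.0, 2.0, 3.0 | 8%, 17%, 34% |
| 20 points | 2.0, 4.0, 6.0 | 18%, 53%, 87% |
| 30 points | 3.0, 6.0, 9.0 | 34%, 86%, over 99% |

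The nominal rate is 5%. The sign of the gap depends on which arm is the more symptomatic. Under these assumptions, comparing the arms within symptom strata removes the gap, because the CA rate in each stratum is the same in both arms.

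**The case against.** **The list is open.** A reader might infer that symptom status cannot be adjusted for at all. The documents do not support that: the caption leaves room for further variables, and in a retrospective chart review an unlisted item can still be abstracted. What stands is that nothing commits the sites to do so. In a multi-center study, an item with no definition or code may be collected unevenly or not at all.

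**Listed items carry some of the information.** A reader might also infer that nothing in Table 1 reflects symptoms. That goes too far. If symptoms drive treatment, baseline AAD use and cardioversion history partly reflect them. But they are earlier treatment decisions, so they are partial proxies and residual confounding remains plausible.

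**The link from symptoms to ICM choice is an inference.** Section 2.1 mentions ICM detection of asymptomatic AF in cryptogenic stroke, syncope and after CA. Section 4.3 excludes ICMs inserted for the first two reasons and patients ablated before the implant, so that sentence largely describes patients outside this cohort. The documents attribute ICM choice only to the physician. This objection stands: neither the existence nor the direction of an imbalance is shown. It is also a reason to record the item, since otherwise balance cannot be examined.

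**The size is assumed.** This stands too. At small imbalances the false-positive rate is close to nominal. The calculation also ignores the crossover from traditional monitoring to ICM that section 9.1 allows.

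**Section 9.4 names no covariates for anything.** This is correct, so collecting the item is not enough by itself. But a later adjustment can use only what was abstracted, so both gaps need closing.

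**Conclusion.** The point holds as a gap in the plan, not as a demonstrated bias. Symptom status at entry is a credible confounder of time to CA, AAD initiation and redo ablation, and the plan does not assure that it can be checked or adjusted for.

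The possible size runs from slight to decisive: a false-positive rate of about 6% to 12% at a 5-point imbalance, about 72% in the worked case, and over 95% near 30 points when the symptom effect is strong. Even at 30 points, a weak symptom effect (40% v 30%) gives only about 34%. All of these rest on assumed CA rates and imbalances, and the direction is unknown. The change should be made before abstraction starts, because adding the item later means reopening up to 2500 charts.

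**What to change.** 1. Add one row to Table 1: *AF symptoms at entry: 0 = asymptomatic, 1 = symptomatic, 9 = not stated*, abstracted from the entry-visit note, with a short written definition common to all sites.
2. Report its distribution by arm, including the share coded 9.
3. In section 9.4, state the covariate set for the Cox models of time to CA, AAD initiation, redo ablation and AF hospitalization: symptom status together with the baseline variables already in Table 1. Baseline AAD use would instead define who is at risk for AAD initiation.
4. Report these outcomes within symptom strata as well.

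**Cost.** One more field per chart and a covariate list that section 9.4 now lacks. Table 1 gives times in days for CA and redo ablation but only yes/no codes for attempted AAD and AF hospitalization, so Cox models for those two also need event dates. Some notes will not state symptoms, perhaps more often in one arm. Confounding may remain among patients coded 9, which is why their share should be shown by arm.

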## 9 STATISTICAL CONSIDERATIONS

### 9.1 General Design Issues

The null hypothesis is that there is no difference in outcomes between patients who underwent ICM insertion versus more traditional monitoring methods. Patients who start with traditional monitoring can cross into the ICM group at any time throughout the study. Primary and secondary endpoints are described below.

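### Table 1 lists the complication outcomes as undated yes/no flags and gives no date of ICM insertion, while crossover into ICM is open and has no attribution rule

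*Combined protocol and SAP*

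**What the plan says.** Table 1 in section 6.1 lists "Stroke and TIA", "Bleeding Complication", "AF-Related Hospitalization" and "HF-Related Hospitalization", each coded only 0 or 1. By contrast, "Time to Catheter Ablation" is recorded in days, as is the time to redo ablation. OAC appears as two undated flags, compliance and "Continued OAC Use". The table has no field for the date of ICM insertion and none for the start or stop date of OAC or AAD. Its caption says that the list is not exhaustive.

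On exposure, section 9.1 states: "Patients who start with traditional monitoring can cross into the ICM group at any time throughout the study". No section says whether such patients are analysed by their initial method, by their final method, or as changing exposure during follow-up.

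Section 9.3 makes thromboembolic events, bleeding, AF and cardiovascular hospitalization and heart failure exacerbation secondary outcomes. Section 9.4 says: "Cox proportional regression models will be used for hazard ratios and confidence intervals". It adds Kaplan-Meier graphs where appropriate and chi-square tests for categorical variables.

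**The concern.** Section 1.2 sets out to compare AF-related complications with and without an ICM. For a patient who starts on Holter, is admitted for AF at month 4 and receives an ICM at month 5, that comparison depends on which came first. The listed fields do not record the order. If the patient is then counted as an ICM patient, an admission that the device could not have influenced is charged to it.

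Under section 4.2 the treating physician decides on insertion. If a clinical event sometimes prompts that decision, which is plausible although the documents do not say so, pre-device events would move into the ICM group selectively. A difference between groups could then appear without any effect of monitoring.

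The missing dates also limit the method of analysis. A 0/1 flag without a time supports a comparison of proportions, but not a hazard ratio or a Kaplan-Meier curve.

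**Working it through.** **What the plan allows to be checked.** It gives no event rate, crossover rate or attribution rule, so it has no figure of its own to reproduce here. The 99% power in section 9.2 does not bear on the point. The group size of 1250 comes from sections 4.1.2 and 9.2. Everything else below is an assumption, used only to show how the bias behaves.

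**Fields set against needs.**
- Placing an event before or after the device needs the event date and the insertion date. Table 1 lists neither.
- Cox or Kaplan-Meier analysis needs the time to first event. Table 1 gives times for ablation and redo ablation only.
- OAC status at a bleed or stroke needs OAC start and stop dates. Table 1 has two undated flags.
- Section 9.3 names the times of AAD and OAC initiation as primary outcomes. Table 1 has no matching field.

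**Illustration of the bias.** Assumptions:
- 20% of each starting group has an AF hospitalization within 12 months, so 0.20 × 1250 = 250 events per group.
- The ICM has no effect.
- 10% of non-ICM starters cross, so 0.10 × 1250 = 125 patients.
- *k* of these 125 had their event before insertion, and none has a first event afterwards.
- Patients are counted in their final group.

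The observed proportions are then

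non-ICM = (250 − *k*)/(1250 − 125) = (250 − *k*)/1125

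ICM = (250 + *k*)/(1250 + 125) = (250 + *k*)/1375

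The pooled proportion is 500/2500 = 0.20, so SE = √(0.20 × 0.80) × √(1/1125 + 1/1375) = 0.4 × 0.0402 = 0.0161.

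| Crossers with a prior event (*k*) | Non-ICM | ICM | z |
|---|---|---|---|
| 25 of 125 (20%, the base rate) | 225/1125 = 20.0% | 275/1375 = 20.0% | 0 |
| 31 of 125 (25%) | 219/1125 = 19.5% | 281/1375 = 20.4% | 0.6 |
| 62 of 125 (half) | 188/1125 = 16.7% | 312/1375 = 22.7% | 3.72 |

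The last row corresponds to p of about 0.0002 with no true effect. In the first row the comparison is unbiased, although 25 of the 275 events labelled ICM (9%) came before the device. Below 25 the sign would reverse. The result therefore turns on how often an event precedes insertion, and the undated flags cannot show that.

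**The case against.** The strongest reply is that Table 1 is not the whole data set. Its caption says so, and it also lacks fields that the study plainly needs, such as the study arm and cardiovascular mortality. Other sections point towards some timing. Section 9.3 wants the times of AAD and OAC initiation. Section 5.1 reviews charts for management changes. The exclusion in section 4.3 for ablation before ICM implant requires the order of those two procedures. This stands: the fault is a gap in specification, and a reader who infers that the dates will not be collected goes beyond the documents. But none of these passages commits sites to dating the complications or the crossover, and several centers working from an open-ended list need not abstract the same dates.

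Four further inferences are tempting and are not supported:

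- *That the problem cannot be repaired later.* Section 5.1 records the initial monitoring method. Analysis by that method keeps pre-device events out of the ICM group without any dates, at the price of diluting an on-device effect. Charts could also be reopened, since section 11.2 keeps an identification log. The plan does not choose the initial-method analysis, however, and returning to charts costs more than abstracting once.
- *That Cox models are promised for these outcomes.* Section 9.4 does not assign them outcome by outcome, and its chi-square tests suit 0/1 flags. What holds is that, with the listed fields, these outcomes could not enter a time-to-event analysis.
- *That no event can be placed on or off OAC.* A patient whose OAC status never changed could be classified if the flags showed this. Event rates by OAC status are also not a stated objective.
- *That events are known to trigger insertion.* No section says so. Section 4.3 excludes ICMs inserted for cryptogenic stroke or syncope, which closes one such route, and nothing suggests that a bleed would prompt an ICM. The argument is most plausible for AF hospitalization.

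**Conclusion.** The concern holds as a gap in the data specification combined with a missing attribution rule. Followed as listed, the plan allows pre-device events of crossers to be counted under ICM, and it leaves four complication outcomes without the times that a Cox or Kaplan-Meier analysis needs.

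The size of the bias is unknown. It affects crossers only, and only if they are counted as ICM patients for the whole of follow-up. The 16.7% versus 22.7% contrast is the upper end of an illustration and not an estimate. It requires half of the crossers to have had a prior event against an assumed base rate of 20%, and classification by final group. None of these inputs is in the documents, so a reader should not take the small p-value as a property of this study. The correction is cheap enough to make without knowing the size.

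**What to change.** Before chart abstraction starts:

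1. In Table 1, add to each of the four flags (stroke/TIA, bleeding, AF hospitalization, HF hospitalization) the date of first event, or days from the index date.
2. Add the date of ICM insertion and the start and stop dates of OAC and AAD. The drug dates also supply the initiation times that section 9.3 already asks for.
3. In section 9.4, treat ICM as a time-dependent exposure: events and person-time before insertion count as non-ICM, and those after insertion as ICM. Name the outcomes to which the Cox models apply.
4. Add analysis by initial monitoring method as a sensitivity analysis.

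Reporting stroke and bleeding by OAC status at the event would be an optional descriptive addition.

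The cost is modestly longer abstraction from charts that are being opened anyway, and some drug-change dates will be approximate. Patient care is not affected.

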## 6.2 Randomization

No randomization will occur due to the nature of the study.

## 6.3 Follow-up Visits

Follow-up will occur up to 12 months after enrollment into the study. Follow-up visits and management changes will occur at the treating physician's discretion.

## 7 SAFETY ASSESSMENTS

There are no safety concerns for this study. Adverse AF, AAD, OAC, and ICM insertion events will be noted as outcomes.

## 8 INTERVENTION DISCONTINUATION

The study will only be discontinued if instructed by the IRB, primary investigator, or other oversight organization.

## 9 STATISTICAL CONSIDERATIONS

### 9.1 General Design Issues

The null hypothesis is that there is no difference in outcomes between patients who underwent ICM insertion versus more traditional monitoring methods. Patients who start with traditional monitoring can cross into the ICM group at any time throughout the study. Primary and secondary endpoints are described below.

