## **1 STUDY OBJECTIVES**

### **1.1 Primary Objective**

- Evaluate the differences in outcomes between implantable cardiac monitors (ICM) and routine management in patients with atrial fibrillation (AF).
- Freedom from AF and continued anti-arrhythmic drug (AAD) and oral anticoagulation (OAC) use following ICM implantation.

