### **1.2 Secondary Objectives**

- To evaluate differences in catheter ablation (CA) and AAD for rhythm control and AF-related complications in those with and without ICM.

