## **3 STUDY DESIGN**

We propose a multi-center, retrospective study to evaluate the use of ICM versus traditional, non-ICM methods such as ECGs, Holter, and mobile cardiac outpatient telemetry (MCOT) units, referred to as non-ICM from here on out, from 2018 to 2021. The primary outcome will be the evaluation of AF freedom at 12 months with continued AAD and OAC use. Secondary outcomes are described above. This study will be approved by the Institutional Review Board (IRB), and patient consent will not be required due to the nature of the study.

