### **4.3 Exclusion Criteria**

- Patients < 18 years of age
- Presence of a permanent pacemaker, implantable cardiac defibrillator, or cardiac resynchronization therapy
- Unable to tolerate ICM or traditional monitoring with ECG, Holter, or MCOT monitoring
- Unable to tolerate AAD, OAC, and CA as part of AF standard of care
- ICM inserted for cryptogenic stroke or syncope
- Was not followed > 12 months
- CA performed for AF before ICM implant

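### Excluding ablation before ICM implant, while patients may cross to ICM at any time, lets a later implant decide whether an earlier ablation counts in Time to CA

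*Combined protocol and SAP*

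**What the plan says.** - Section 9.1 (General Design Issues): "Patients who start with traditional monitoring can cross into the ICM group at any time throughout the study".
- Section 4.3 (Exclusion Criteria): "CA performed for AF before ICM implant". The anchor is the implant, not entry to the study, and no time limit is given. Only a patient who receives an ICM can meet it.
- Section 9.3 lists Time to CA among the primary outcomes. Table 1 (Section 6.1) records it in days without an origin.
- Section 6.3: "Follow-up will occur up to 12 months after enrollment into the study". Neither it nor Section 5.1 ties enrollment to a chart date, although the study is retrospective.
- Section 5.1: "Charts of patients enrolled in the study will be reviewed for an initial monitoring method". The initial method is abstracted but is not named as the analysis exposure.
- Section 1.1 points to another clock: "Freedom from AF and continued anti-arrhythmic drug (AAD) and oral anticoagulation (OAC) use following ICM implantation".
- Section 9.4 specifies Cox models without saying how a crosser's time before implant is classified.

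**The concern.** Take two patients who start on conventional monitoring and are both ablated at month 4. One never receives an ICM and stays in the non-ICM arm as an event. The other is implanted at month 8, meets the exclusion and is deleted. The two histories are identical up to and including the outcome. What separates them is an exposure that came afterwards.

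Two distinct biases can follow:

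- **(a) Exclusion bias.** Some events are removed from patients who started without an ICM, and none from patients who had one at the start.
- **(b) Immortal-time bias.** If crossers are counted as ICM from enrollment, the retained crossers had to be free of CA until their implant, and that event-free time is credited to ICM.

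The two push in opposite directions. The plan does not settle which applies, so an apparent effect of ICM on Time to CA, in either direction, could come from the bookkeeping alone.

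**Working it through.** **Plan figure.** The plan gives no CA, crossover or post-CA implant rate, so there is no figure of its own to reproduce here. Every rate below is an assumption.

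**Hand check of one case.** From the plan: N = 2500 and 12 months. Assumed: 40% on ICM at entry (1000 patients, 1500 not), 30% CA by 12 months, 20% of the rest implanted by 12 months, constant hazards, equal implant hazard before and after CA, and no ICM effect.

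- CA hazard λ = −ln 0.70 = 0.3567 per year. Implant hazard μ = −ln 0.80 = 0.2231. Sum = 0.5798. 1 − exp(−0.5798) = 0.44.
- Implanted before CA: (0.2231/0.5798) × 0.44 = 0.1693, or 254 of 1500.
- CA, then implant (deleted): 0.20 − 0.1693 = 0.0307, or 46 of 1500 (1.84% of 2500; a simulation gives 1.82%).
- Implant, then CA: 0.30 − (0.3567/0.5798) × 0.44 = 0.0293, or 44 of 1500.

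The cumulative-hazard ratio, −ln(1 − risk) in ICM over non-ICM, approximates the hazard ratio (HR):

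1. *Crossers as ICM from enrollment.* ICM: (300 + 44)/(1000 + 254) = 27.4%. Non-ICM: 1200 never implanted, 360 events, 30%. HR ≈ 0.3207/0.3567 = 0.90 (simulated 0.89).
2. *Initial method.* Non-ICM: (450 − 46)/(1500 − 46) = 27.8%. ICM: 30%. HR ≈ 0.3567/0.3255 = 1.10 (simulated 1.10).
3. *Time-varying ICM.* Non-ICM time is 1500 × 0.44/0.5798 = 1138 years, less about 14 for the 46 deleted (mean 0.31 year each), or 1124. Rate 360/1124 = 0.320. HR ≈ 0.3567/0.320 = 1.11 (simulated 1.11).
4. *ICM clock started at implant.* Both arms have hazard 0.3567, so HR = 1.00 (simulated 1.00).

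If nobody is implanted after CA, the exclusion deletes no one. Rule 1 then compares 27.4% with (450 − 44)/(1500 − 254) = 32.6%, so HR ≈ 0.3207/0.3943 = 0.81 (simulated 0.80). That is immortal time alone.

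**Wider simulation.** True HR 1.00, N = 2500, 30% CA, 1000 replicates. Seven assumed cases of ICM at entry / crossing by the rest: 40/10, 40/20, 30/30, 20/40, 50/10, 50/20 and 50/40%. The exclusion is applied as written. Cells give the HR range, with false positives at two-sided 0.05.

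| Rule | No implant after CA | Equal hazard | 3 times hazard after CA |
|---|---|---|---|
| 1. ICM from enrollment | 0.57-0.91 (26-100%) | 0.72-0.96 (8-98%) | 1.04-1.38 (8-92%) |
| 2. Initial method | 0.99-1.00 (4-6%) | 1.05-1.22 (10-71%) | 1.15-1.68 (44-100%) |
| 3. Time-varying | 1.00 (4-5%) | 1.05-1.27 (10-83%) | 1.15-2.01 (46-100%) |
| 4. Clock at implant | 0.78-0.95 (11-94%) | 1.00 (5-6%) | 1.10-1.57 (24-100%) |

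A separate simulation at equal hazard (40% on ICM at entry, 15-45% CA, 10-40% crossing) gives 0.83-0.95, 1.05-1.23, 1.05-1.28 and about 1.00 for rules 1-4. Without the exclusion, rules 1-3 return 0.99-1.01.

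**After the fix.** With the exclusion moved to a common index date, the initial-method and time-varying models each give 0.99-1.01 (4-6% false positives) at every post-CA implant rate tried.

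**The case against.** **The exclusion may mean CA before entry.** Section 4.1.2 enrolls patients who satisfy the criteria at screening, and Section 5.1 treats later CA as an outcome. Under that reading bias (a) disappears. This stands as a reading, so the defect may be one of wording. But Section 4.3 names the implant, which for a crosser can fall after entry. Bias (b) would also remain under rule 1 whenever implant is less likely after CA.

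**The plan's own clock may be harmless.** Section 1.1 refers to outcomes after implantation, which is rule 4, and that gives 1.00 at equal hazard. This is correct. It fails once the implant hazard changes after CA, and Section 1.1 gives no matching origin for the non-ICM arm.

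**The extremes are overstated.** A reader might credit the lowest hazard ratios to the exclusion. They occur where it removes no one. The highest come partly from cases far from the 1:1 target in Section 9.2: under rule 1 at three times the hazard, the 50/40 case puts about 72% of patients in the ICM arm, and the four cases nearer 1:1 give 1.04-1.13. With 50/40 and equal hazard, rule 1 gives 0.87, against 0.72 in the 20/40 case.

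**The restriction may be deliberate.** Section 2.1 mentions ICM detection "including asymptomatic AF in cryptogenic stroke, syncope, and after CA", and Section 4.3 excludes all three settings. That sentence describes earlier studies, so it shows only that implants after CA are plausible here. The intent may be sound. For time to a first CA, however, an implant after the event adds no ICM time, so keeping these patients does not undo it.

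**Time to CA may not be primary.** Section 3 says "The primary outcome will be the evaluation of AF freedom at 12 months with continued AAD and OAC use", and Section 1.2 places CA among the secondary objectives. That conflict is a separate matter, and the bias exists whatever the outcome's rank.

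**Conclusion.** The concern holds for the exclusion as written. With crossing allowed at any time, eligibility depends on whether an event of Time to CA preceded a later exposure. With no true effect, equal implant hazard and 10-40% crossing, the hazard ratio is about 1.05-1.3 by initial method or time-varying ICM, about 1.00 with the clock at implant, and about 0.72-0.96 with crossers counted as ICM from enrollment. With no implants after CA, that last rule gives about 0.57-0.91 although the exclusion removes no one. At 10% crossing the null range over all four rules is about 0.9-1.16.

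A reader might infer that the result will be biased in a known direction or by a known amount. The documents do not support that: they give none of the rates, and the sign reverses with the counting rule. Nor do they show that implant dates will go uncollected, since Table 1 is expressly not exhaustive. Only Time to CA has been quantified here. The result assumes constant hazards and, in these null runs, crossing driven by nothing but time and prior CA.

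**What to change.** 1. **Sections 4.1, 5.1, 6.3, 9.3:** define one chart-based index date for both arms, for example the date the initial monitoring method was chosen at the first AF visit in 2018-2021. Start follow-up and Time to CA there.
2. **Section 4.3:** replace the exclusion with CA for AF before the index date, applied to both arms. Keep patients ablated between the index date and implant.
3. **Sections 9.1 and 9.4:** state that pre-implant time is never counted as ICM time. Name as primary either the Cox model by monitoring method at the index date or the Cox model with time-varying ICM, with the other as sensitivity analysis. Adjust both for the Table 1 baseline variables.
4. **Table 1:** add the index and implant dates. Report how many patients crossed and how many were implanted after CA.

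Items 2 and 3 must change together: both models stay biased under the present exclusion if anyone is implanted after CA.

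**Cost.** Wording, two date fields and re-abstraction of charts excluded under the old rule (20-117 of 2500 in the simulation at equal hazard, 55-258 at three times). The insertion lists in Section 4.1.1 may supply implant dates.

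The choice of primary model is a trade-off. With a true HR of 1.30 (assumed), the initial-method model dilutes it to about 1.23-1.29 with power 69-95%; the time-varying model gives 1.30 with 94-97%. If recurrence raises both implant and CA hazards 2-3 fold, the time-varying model gives a null HR of 1.00-1.12 (5-31% false positives), against 0.99-1.01 (4-7%) by initial method. Neither removes confounding by physician choice of ICM beyond the Table 1 variables.
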